18.4.2. ECG MARKEDLY ABNORMAL CRITERIA

Absolute values of the QT interval will be classified as:

- >=450 msec
- >=480 msec
- >=500 msec

The change from Baseline of QT interval will be classified as:

- >30 msec increase from baseline
- >60 msec increase from baseline

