#### **9.4.2 Vital Signs Measurements, Physical Findings, and Clinical Laboratory Evaluations**

Summaries and listings of data for vital signs, hematology, clinical chemistry, and urinalysis laboratory tests, ECGs and physical examination findings will be presented. Appropriate descriptive statistics will be summarized for the observed value at each scheduled assessment and for the corresponding change from baseline.

For hematology and clinical chemistry tests, listings of patient data will also flag up any abnormal or out-of-range values. Clinically significant changes in the laboratory test parameters will be summarized and listed. Hematology and clinical laboratory data will be reported in System International units.

For ECG variables, the QT correction factor will be based on both the Bazett and Fridericia formulae (QTcB and QTcF). Categorical summaries of absolute QT, QTcB and QTcF values and change from (baseline) values in QT, QTcB and QTcF values will be presented by treatment and visit.

Descriptive statistics will be used to present the safety outcomes including, physical examination results, weight, BMI, vital signs measurements, clinical laboratory test results, and ECG results. Change from baseline will also be summarized for vital signs measurements, clinical laboratory test results.

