3.3. CHANGES TO ANALYSIS FROM PROTOCOL

No changes from the analysis planned in the protocol were made.

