18.4. ECG EVALUATIONS

The following ECG parameters will be summarized:

- o Heart Rate (bpm)
- o PR Interval (msec)
- o QRS Interval (msec)
- o QT Interval (msec)
- o QTcB (msec) {based on Bazett formula}
- o QTcF (msec) {based on Fridericia formula}

The actual and change from baseline values for the above parameters will be summarized using descriptive statistics (n, mean, SD, median, and range) by treatment and all available visits.

The overall assessment of ECG will be summarized using frequency and percentage of the following indications:

- o Normal
- o Abnormal, Not Clinically Significant (ANCS)
- o Abnormal, Clinically Significant (ACS)

A listing of ECG parameters and of the overall assessment will be provided.

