Parameter (Unit)	Visit	Statistics	ANB020 (N=XX)		Placebo (N=XX)		Total (N=XX)
			Actual	Change from Baseline	Actual	Change from Baseline	
Heart Rate (bpm)	Baseline	n	xx	-	xx	-	xx
		Mean (SD)	xx x (xx xx)	-	xx x (xx xx)	-	xx x (xx xx)
		Median	xx x	-	xx x	-	xx x
		Min, Max	xx, xx	-	xx, xx	-	xx, xx
	Day 45	n	xx	xx	xx	xx	xx
		Mean (SD)	xx x (xx xx)	xx x (xx xx)	xx x (xx xx)	xx x (xx xx)	xx x (xx xx)
		Median	xx x	xx x	xx x	xx x	xx x
		Min, Max	xx, xx	xx, xx	xx, xx	xx, xx	xx, xx
PR Interval (msec)	-----						
QRS Interval (msec)	-----						
QT Interval (msec)	-----						
QTc Interval (msec)	-----						
QTcB (msec)	-----						
QTcF (msec)	-----						

Source: Listing 16 3 6 1

Note:

- N is the number of patients within each treatment group under Safety Analysis Set
- Baseline is defined as the nearest non-missing value before first dose of study medication

Programming Note (not part of table): Continue the table for all parameters and all available visits

Document: \\ieedc-nas01a\\biosdata\\AnaptysBio\\ANB020\\CYA74393\\Biostatistics\\Documentation\\SAP\\Draft\\2018-02-07
Author: [REDACTED]

Version Number: Draft 3.0
Version Date: 07Feb2018

Table Shells

AnaptysBio Inc.
PROTOCOL ANB020-003
Page 34 of 42

Table 14 3 5 2
Overall ECG and QT Changes from Baseline – Safety Analysis Set

Category	Visit	Indication	ANB020 (N=XX)	Placebo (N=XX)	Total (N=XX)	
Overall Assessment of ECG	Baseline	Nomal	xx (xx x)	xx (xx x)	xx (xx x)	
		Abnormal NCS	xx (xx x)	xx (xx x)	xx (xx x)	
		Abnormal CS	xx (xx x)	xx (xx x)	xx (xx x)	
		Missing	xx (xx x)	xx (xx x)	xx (xx x)	
	Day 45	Nomal	xx (xx x)	xx (xx x)	xx (xx x)	
		Abnormal NCS	xx (xx x)	xx (xx x)	xx (xx x)	
		Abnormal CS	xx (xx x)	xx (xx x)	xx (xx x)	
		Missing	xx (xx x)	xx (xx x)	xx (xx x)	
Patients reaching a value in QT Interval (msec) at any time during treatment above or equal to [1]		≥ 450 (msec)				
		≥ 480 (msec)				
		≥ 500 (msec)				
Patients Experiencing an increase in QT Interval (msec) at any Time During Treatment by more than [1] [2]		>30 (msec)				
		>60 (msec)				
Patients Experiencing a decrease in QT Interval (msec) at any Time During Treatment by more than [1] [2]		>30 (msec)				
		>60 (msec)				

Source: Listing 16 3 6

Note:

- N is the number of patients within each treatment group under Safety Analysis Set
- Percentages are based on number of patients within each treatment group under Safety Analysis Set (N)
- NCS – Not Clinically Significant, CS – Clinically Significant

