- [1] Cumulative counts, [2] Change from baseline to any observation on treatment

Programming Note (not part of table): Use all relevant visits and parameters

Document: \\ieedc-nas01a\\biosdata\\AnaptysBio\\ANB020\\CYA74393\\Biostatistics\\Documentation\\SAP\\Draft\\2018-02-07
Author: [REDACTED]

Version Number: Draft 3.0
Version Date: 07Feb2018

Table 14 3 6 1
Vital Signs – Safety Analysis Set

Parameter (Unit)	Visit	Time Point	Statistics	ANB020 (N=XX)		Placebo (N=XX)		Total (N=XX)
				Actual	Change from Baseline	Actual	Change from Baseline	
Pulse Rate (bpm)	<Visits>	<Time Point>	n	xx	-	xx	-	xx
			Mean (SD)	xx x (xx xx)	-	xx x (xx xx)	-	xx x (xx xx)
			Median	xx x	-	xx x	-	xx x
			Min, Max	xx, xx	-	xx, xx	-	xx, xx
Respiratory Rate (resp/min)	<Visits>							
Body Temperature (°C)	<Visits>							
Body Temperature (°F)	<Visits>							
Systolic Blood Pressure (mmHg)	<Visits>							
Diastolic Blood Pressure (mmHg)	<Visits>							

Source: Listing 16 3 7 1

Note:

- N is the number of patients within each treatment group under Safety Analysis Set
- Baseline is defined as the nearest non-missing value before first dose of study medication

Programming Note (not part of table): Continue the table for all parameters and all available visits

Table 14 3 7 1
Spirometry – Safety Analysis Set

Parameter (Unit)	Visit	Statistics	ANB020 (N=XX)		Placebo (N=XX)		Total (N=XX)	
			Actual	Change from Baseline	Actual	Change from Baseline	Actual	Change from Baseline
Actual FEV ₁ (L)	<Visits>	n	xx	-	xx	-	xx	-
		Mean (SD)	xx x (xx xx)	-	xx x (xx xx)	-	xx x (xx xx)	-
		Median	xx x	-	xx x	-	xx x	-
		Min, Max	xx, xx	-	xx, xx	-	xx, xx	-
Predicted FEV ₁ (L)	<Visits>							
Percent of Predicted (%)	<Visits>							

Source: Listing 16 3 8 1

Note:

- N is the number of patients within each treatment group under Safety Analysis Set
- Baseline is defined as the nearest non-missing value before first dose of study medication

Programming Note (not part of table): Continue the table for all parameters and all available visits

Table Shells

AnaptysBio Inc.
PROTOCOL ANB020-003
Page 37 of 42

Table 14 3 7 2
Ashtma Assessment of Symptom Control – Safety Analysis Set

Category	Visit	Indication	ANB020 (N=XX)	Placebo (N=XX)	Total (N=XX)
Patients with Asthma Symptoms More than Twice a Week	Baseline	Yes	xx (xx x)	xx (xx x)	xx (xx x)
		No	xx (xx x)	xx (xx x)	xx (xx x)
Patients Who Woke in Night due to Asthma	Day 14	Yes	xx (xx x)	xx (xx x)	xx (xx x)
		No			

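### The protocol plans categorical summaries of QT, QTcB and QTcF, but the SAP and its table shell categorise uncorrected QT only and declare no change

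*SAP*

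**What the plan says.** Protocol 9.4.2 says that QT will be corrected by both the Bazett and the Fridericia formulae. It plans categorical tables, in which "absolute QT, QTcB and QTcF values and change from (baseline) values in QT, QTcB and QTcF values will be presented by treatment and visit". It gives no cut-offs. Protocol 9.0 leaves the details of the methods to the SAP and says that any change to them will be documented there.

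SAP 18.4 names QT, QTcB ("QTcB (msec) {based on Bazett formula") and QTcF as separate parameters and gives all of them descriptive statistics. SAP 18.4.2, which sets the categories, covers QT alone:

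- Absolute values: "Absolute values of the QT interval will be classified as" at least 450, 480 and 500 msec.
- Change: "The change from Baseline of QT interval will be classified as" an increase above 30 or above 60 msec.

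Table shell 14.3.5.2 follows the same pattern. Its absolute rows read "Patients reaching a value in QT Interval (msec) at any time during treatment above or equal to" and its change rows read "Patients Experiencing an increase in QT Interval (msec) at any Time During Treatment by more than". It adds rows for decreases, again for QT. A programming note says "Use all relevant visits and parameters".

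SAP 3.3 states: "No changes from the analysis planned in the protocol were made".

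**The concern.** The SAP narrows a planned safety analysis from three measures to one while stating that nothing was changed. The measure kept is the one that is not corrected for heart rate. QT shortens as the heart speeds up, so a fixed QT cut-off can miss a patient whose corrected interval is long at a faster rate. It can also count a patient with a slow rate whose corrected interval is below the cut-off. ECGs are among the primary safety endpoints in Protocol 9.4, and the outlier table is where a reader would look for the number of patients with a prolonged interval.

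**Working it through.** **Planned against specified**

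| Measure | Absolute: protocol | Absolute: SAP and shell | Change: protocol | Change: SAP and shell |
|---|---|---|---|---|
| QT | yes | yes | yes | yes |
| QTcB | yes | no | yes | no |
| QTcF | yes | no | yes | no |

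Planned: 3 measures × 2 types = 6. Specified: 1 × 2 = 2. Missing: 6 − 2 = 4.

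**Is it a version effect?** The SAP cites Amendment 3. The change logs for Amendments 4 and 5 list nothing for Protocol 9.4.2, so later amendments do not explain the gap.

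**Could QT in SAP 18.4.2 be shorthand for all three?** SAP 18.4 and Table 14.3.5.1 list QT, QTcB and QTcF separately, so that reading is not natural.

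**Can the omission change who is counted?** The documents contain no ECG data. The heart rates and QT values below are assumed, and they show that disagreement is possible, not how often it happens. The formulas use the standard roots: RR = 60/HR in seconds, QTcB = QT/RR^(1/2), QTcF = QT/RR^(1/3).

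| Assumed values | Raw QT result | QTcB | QTcF |
|---|---|---|---|
| HR 80, QT 420 (RR 0.750) | no category | 485.0 | 462.3 |
| HR 90, QT 400 (RR 0.667) | no category | 489.9 | 457.9 |
| HR 50, QT 460 (RR 1.200) | counted as at least 450 | 419.9 | 432.9 |
| HR 60, QT 400 to HR 90, QT 380 | −20, not counted | +65.4 | +35.0 |
| HR 75, QT 380 to HR 55, QT 420 | +40, counted as above 30 | −22.7 | −1.3 |

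The raw QT at which the corrected value reaches 450 msec is 450 × RR^(1/2) for Bazett and 450 × RR^(1/3) for Fridericia:

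| HR (bpm) | Bazett | Fridericia |
|---|---|---|
| 50 | 493.0 | 478.2 |
| 60 | 450.0 | 450.0 |
| 80 | 389.7 | 408.9 |
| 100 | 348.6 | 379.5 |

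At 60 bpm the choice of measure makes no difference. Away from 60 bpm a QT cut-off of 450 msec is a different criterion from a QTc cut-off of 450 msec.

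**Dependence on the roots.** In the text available for this review, SAP 18.4.1 shows a cube root for QTcB and a fourth root for QTcF. This may come from reading the PDF. With those roots, HR 80 and QT 420 gives 462.3 and 451.3 msec, still at least 450 on both. HR 50 and QT 460 gives 432.9 and 439.5, still below 450 on both. HR 90 and QT 400 gives 457.9 and 442.7, so there only the first crosses. Miscounting in both directions is possible under either set of roots.

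**The case against.** The strongest objection is that almost nothing is lost. Protocol Table 4.1 schedules ECGs at screening and Day 45, or at early termination, so each patient normally has one post-dose value, in about 15 patients on ANB020 and 5 on placebo. Table 14.3.5.1 prints the minimum and maximum of QTcB and QTcF by arm, for actual values and for change, so a reader can see whether anyone crossed a cut-off. The ECG listing then allows a count by hand. Its shell names QTcF explicitly, and QTcB follows from the instruction there to present all parameters. The investigator reviews each ECG, with QTc among the recorded parameters (Protocol 7.1.3). SAP 18 plans no between-group tests for safety data. All of this stands, and it limits the severity. It does not make the planned counts part of the SAP.

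A second objection is that the programming note, "Use all relevant visits and parameters", lets the programmer add QTc rows, and that the table shells are marked as a draft. The note does leave room. But it names neither corrected measure and gives no QTc criteria, and SAP 18.4.2 itself, in a version marked final, covers only QT.

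A third objection is that the protocol sets no cut-offs, so applying the listed QT cut-offs to QTc is a choice. That is correct, and the SAP author should make that choice explicitly.

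**Conclusion.** The inconsistency is real, and minor. Four of the six categorical summaries planned in Protocol 9.4.2 have no specification in the SAP, and the statement in SAP 3.3 is inaccurate on this point. Followed as written, the SAP would count outliers only on a value that depends on heart rate, for a listed primary safety endpoint. A planned tabulation is lost, not QTc data, and no decision rule uses it.

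The textual finding needs no assumptions. The statement that counts can differ rests on assumed heart rates and QT values, and says nothing about frequency in this trial.

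**What to change.** - In SAP 18.4.2 and Table 14.3.5.2, add QTcB and QTcF for absolute values and for change from baseline. The cut-offs already listed for QT can be used, if the SAP states that they apply to QTc as well.
- If the QT-only table is intended, declare and justify the departure in SAP 3.3. That corrects the record but leaves the counts on uncorrected QT.
- In the same edit, settle the layout: the protocol asks for summaries by visit, whereas the shell counts patients at any time during treatment.
- Before programming, check the root indices in SAP 18.4.1 against the original page. This is a precaution, not a claimed error.

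The cost is a few rows in one table, from values the SAP already derives. No new data are needed.

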18.5. VITAL SIGNS

The following Vital Signs measurements will be reported for this study:

- Blood Pressure (mmHg)
- Respiratory Rate (resp/min)
- Pulse Rate (breaths/min)
- Temperature (°C or °F)

The actual and change from baseline values for the above parameters will be summarized using descriptive statistics (n, mean, SD, median, and range) by treatment and all available visits.

A listing of the above parameters will be provided.

18.6. PHYSICAL EXAMINATION

The frequency and percentage of patients with physical examination assessments will be summarized by body system and treatment group at each available visit.

A listing of physical examination findings will be provided.

18.7. OTHER SAFETY ASSESSMENTS (SPIROMETRY)

For patients with a history of asthma, the following spirometry or peak flow parameters will be summarized for observed and change from baseline values by treatment group at each available visit:

Actual FEV1

Predicted FEV1

Document: \\ieedc-nas01a\biosdata\AnaptysBio\ANB020\CYA74393\Biostatistics\Documentation\SAP\Final2018-02-07
Author: [REDACTED] Version Number: Final 1.0
Version Date: 07Feb2018

STATISTICAL ANALYSIS PLAN

AnaptysBio Inc
PROTOCOL ANB020-003
Page 29 of 36

Percent Predicted

A detailed listing will be presented for spirometry.

19. PHARMACOKINETIC OUTCOMES

Pharmacokinetic analysis of the plasma concentration data for ANB020 will be performed at IQVIA, Overland Park, Kansas, United States. The actual sampling times will be used in the PK parameter calculations, and PK parameters will be derived using standard non-compartmental methods using Phoenix WinNonlin® 6.4 or higher (Pharsight Corp., Certara Company, Princeton, New Jersey, United States); and/or SAS® Version 9.2 or higher. Graphics may be prepared with SAS® Version 9.2, or higher; SigmaPlot® 12.5, or higher (Systat Software, Inc., San Jose, California, United States); or Phoenix WinNonlin® 6.4, or higher.

A listing of PK blood sample collection times as well as derived sampling time deviations will be provided. A subject listing of all concentration-time data for ANB020 will be provided.

Concentration data of ANB020 will be summarized by treatment and nominal time point using the number of observations (n), and number of observations \geq lower limit of quantitation (LLOQ), arithmetic mean, SD, CV, minimum, median, and maximum. Concentrations below the lower limit of quantitation (BLQ) will be treated as zero for calculation of descriptive statistics. If the calculated mean concentration is BLQ, the mean value will be reported as BLQ and the SD and CV will be reported as not applicable (NA). Missing data will not be interpolated. If 1 or more concentrations at a given time point are missing, they will be reported as missing and will be omitted from the calculation of descriptive statistics.

Plots of the mean plasma concentration-time profile for ANB020 will be presented by nominal sampling time on linear and semi-logarithmic scales. Individual concentration-time data will be listed and plotted by actual sampling times on linear and semi-logarithmic scales.

For the calculation of PK parameters, concentrations that are BLQ will be assigned a value of zero if they precede quantifiable samples prior to t_{max} . Any anomalous concentration values observed at pre-dose will be identified in the study report and will be used for the computation of PK parameters if the anomalous value is not greater than 5% of C_{max} . If the anomalous value is greater than 5% of C_{max} , the PK parameters for the given subject will be included in listings but excluded from summary presentations and analyses. Following C_{max} , BLQ values embedded between 2 quantifiable data points will be treated

Document: \\ieedc-nas01a\biosdata\AnaptysBio\ANB020\CYA74393\Biostatistics\Documentation\SAP\Final2018-02-07
Author: [REDACTED] Version Number: Final 1.0
Version Date: 07Feb2018

STATISTICAL ANALYSIS PLAN

AnaptysBio Inc
PROTOCOL ANB020-003
Page 30 of 36

as missing. Trailing BLQ values (BLQ values after the last quantifiable concentration) will be set to zero. If consecutive BLQ concentrations are followed by quantifiable concentrations in the terminal portion of the concentration curve, these quantified values will be excluded from the PK analysis by setting them to missing.

The following PK parameters will be computed for ANB020, if data permits:

C_{max}	Maximum concentration in serum ($\mu\text{g/mL}$), obtained directly from the observed concentration versus time data.
t_{max}	Time of maximum concentration (h), obtained directly from the observed concentration versus time data.
$AUC_{(0-\infty)}$	Area under the concentration-time curve in serum from time zero (predose) extrapolated to infinite time ($\text{h}\cdot\mu\text{g/mL}$), calculated by linear up/log down trapezoidal summation and extrapolated to infinity by addition of the last quantifiable concentration divided by the apparent terminal rate constant: $AUC_{(0-last)} + C_{last}/\lambda_z$.
$AUC_{(0-last)}$	Area under the serum concentration-time curve from time zero to the time of the last quantifiable concentration ($\text{h}\cdot\mu\text{g/mL}$), calculated by linear up/log down trapezoidal summation.
CL	Systemic clearance (L/h), calculated as dose/ $AUC_{(0-\infty)}$.
λ_z	Apparent terminal rate constant ($1/\text{h}$), determined by linear regression of the terminal points of the log-linear concentration-time curve.
$t_{1/2}$	Apparent terminal half-life (h), determined as $(\ln 2/\lambda_z)$.
V_{ss}	Volume of distribution at steady state following intravenous dosing (L), calculated as mean residence time (extrapolated to infinity) multiplied by systemic clearance.
V_z	Volume of distribution (L), estimated by dividing the systemic clearance by

Document: \\ieedc-nas01a\biosdata\AnaptysBio\ANB020\CYA74393\Biostatistics\Documentation\SAP\Final2018-02-07
Author: [REDACTED] Version Number: Final 1.0
Version Date: 07Feb2018

Template No: CS_TP_BS016 Revision 4
Effective Date: 01Apr2016

Reference: CS_WI_BS005

STATISTICAL ANALYSIS PLAN

AnaptysBio Inc
PROTOCOL ANB020-003
Page 31 of 36

λ_z .

The following ANB020 PK parameters will be calculated for diagnostic purposes and listed, but will not summarized:

λ_z_lower	Start time (h) of the log-linear regression to determine λ_z and $t_{1/2}$.
λ_z_upper	End time (h) of the log-linear regression to determine λ_z and $t_{1/2}$.
$t_{1/2}$, Interval	The time interval (h) of the log-linear regression to determine λ_z and $t_{1/2}$, calculated as $\lambda_z_upper - \lambda_z_lower$,
$t_{1/2}$, N	Number of data points included in the log-linear regression analysis used to calculate λ_z and $t_{1/2}$. A minimum of 3 data points is required.
R_{sq}	Coefficient of determination for calculation of λ_z . A minimum of 3 data points (excluding C_{max}) will be used for determination of the terminal linear phase of the concentration-time profile. If the R_{sq} is less than 0.800 then λ_z , $t_{1/2}$, $AUC_{(0-\infty)}$, CL , V_{ss} , and V_z will be listed but not included in summary presentations or analyses.
% AUC_{ex}	Percentage of $AUC_{(0-\infty)}$ obtained by extrapolation, calculated as $[(C_{last}/\lambda_z)/AUC_{(0-\infty)} \times 100]$. If the extrapolated area is greater than 20.0% of $AUC_{(0-\infty)}$, then $AUC_{(0-\infty)}$ will be listed but not included in summary presentations or analyses.

The PK parameters, with the exception of t_{max} , will be summarized by treatment using n, arithmetic mean, SD, CV, minimum, median, maximum, geometric mean (Gmean), and geometric CV (gCV). The PK parameter t_{max} will be reported with n, minimum, median, and maximum only.

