## 18.0 APPENDIX 2: PHARMACOKINETIC/WHOLE BLOOD (SERUM) BIOMARKER TIME POINTS

Study Visit	Pharmacokinetic Sample Time Point (Serum)	Sample Time Point for Biomarker Whole Blood collection for Ex vivo Peanut Challenge (Stanford Univ Only)	Sample Time Point for Leukocytes (Whole blood)	Sample Time point for Biomarker serum collection for Cytokines
Screening (Day-7 to -14)		Screening Peanut ex vivo whole blood sample to be obtained (Baseline) prior to administration of BPCFC d	Collect Prior to administration of BPCFC a	Collect Prior to administration of BPCFC
Day 1 ANB020 Dosing	Pre-Dose (-≤30 minutes)			
	0.50 hours (±5 minutes) post-start of infusion			
	EOI (+≤3 minutes)			
	EOI+3 hours (±10 minutes)			
Day 2	24 hours (±2 hours) post-start of infusion	24 hours (±2 hours) post-start of infusion	24 hours (±2 hours) post-start of infusion	24 hours (±2 hours) post-start of infusion
Day 5	96 hours (±2 hours) post-start of infusion	96 hours (±2 hours) post-start of infusion	96 hours (±2 hours) post-start of infusion	96 hours (±2 hours) post-start of infusion
Day 15 b	336 hours (+112 hours) post-start of infusion		336 hours (+112 hours) post-start of infusion	336 hours (+112 hours) post-start of infusion
Day 45 c	1,056 hours (±48 hours) post-start of infusion. Sample to be obtained prior to administration of BPCFC.		1,056 hours (±48 hours) post-start of infusion. Sample to be obtained prior to administration of BPCFC.	

Abbreviation: EOI = actual time of end of infusion, BPCFC = blind placebo-controlled food challenge.

a Leukocytes will be obtained as part of hematology safety laboratory panel at screening, Day 2, and Day 45/ET. On Day 5 and Day 15, whole blood samples for leukocytes will be collected separately as there is no safety laboratory assessment on Day 5 and Day 15.

- b If the Investigator decides to complete the BPCFC in 2 days, the blood samples scheduled on Day 15 will be collected on Day 16. If the Investigator decides to utilize the +4 day visit window for Day 14 and separate the two challenges to occur over two consecutive days, the blood samples will be collected the day after the last BPCFC challenge.
- c If the patient discontinues from study before Day 45 and returns to site for early termination (ET) visit, the PK sample will be collected at ET visit.

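### SAP 19 withholds AUC(0-inf) when more than 20.0% is extrapolated but keeps CL, Vss and Vz, which are computed from it, so if any patient triggers the rule the PK summaries become inconsistent

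*SAP*

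**What the plan says.** SAP section 19 defines the derived parameters as a chain that starts from AUC(0-inf):

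- CL: "Systemic clearance (L/h), calculated as dose" divided by AUC(0-inf).
- Vss: "calculated as mean residence time (extrapolated to infinity) multiplied by systemic clearance".
- Vz: "Volume of distribution (L), estimated by dividing the systemic clearance by" the terminal rate constant.

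The table of diagnostic parameters in the same section then sets two quality rules in adjacent rows.

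- **R-squared row.** If R-squared "is less than 0.800 then" lambda-z, t1/2, AUC(0-inf), CL, Vss and Vz all leave the summaries.
- **%AUCex row.** "If the extrapolated area is greater than 20.0% of" AUC(0-inf), then AUC(0-inf) alone "will be listed but not included in summary presentations or analyses".

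The paragraph after the table has every PK parameter except tmax summarised in full. No other rule removes CL, Vss or Vz because of extrapolation. The pre-dose rule in SAP 19 (anomalous value above 5% of Cmax) and the major-deviation rule in SAP 11 deal with other problems.

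**The concern.** The R-squared row shows that the authors regard CL, Vss and Vz as sharing the fate of AUC(0-inf). The %AUCex row does not carry that through, and no reason is given. A patient whose AUC(0-inf) is judged too extrapolated to summarise would still contribute three parameters calculated from it.

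The inconsistency would show in the PK parameter table. Every ANB020 patient is planned to receive the same single 300 mg dose. With full doses and the same patients, the geometric mean of CL therefore equals 300 mg divided by the geometric mean of AUC(0-inf). Once a patient is dropped from one row and kept in the other, that identity generally fails and the two rows describe different patients.

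The stakes are limited to the description of PK under the secondary objective.

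**Working it through.** The SAP states no expected %AUCex, so there is no figure of its own to reproduce. The check asks when the rule would trigger.

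**Inputs from the documents**

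- Predicted half-life about 14 days (Protocol 2.1, Clinical studies).
- Last PK sample at "1,056 hours (±48 hours) post-start of infusion" (Protocol Appendix 2). Day 45 gives (45 − 1) × 24 = 1,056 h, or 44 days.
- Previous PK sample on Day 15, at (15 − 1) × 24 = 336 h, or 14 days.
- 15 patients on ANB020 (Protocol 6.2.2).
- Limit of 20.0% (SAP 19).

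**Assumptions not in the documents**

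- Mono-exponential decline.
- Log-normal half-life with median 14 days and a CV shown over a range.

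**Step 1: extrapolated share of AUC.** Under mono-exponential decline, %AUCex = 100 × 2^(−tlast / t1/2).

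- Half-life 14 d, last sample 44 d: 2^(−44/14) = 11.3%. Across the ±48 h window this is 12.5% (42 d) to 10.3% (46 d). The patient passes.
- Half-life 21 d, last sample 44 d: 23.4%. The patient fails.
- Half-life 14 d, Day 15 sample last: 2^(−14/14) = 50%. The patient fails.

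**Step 2: where the limit is crossed.** Setting the share to 20% gives tlast / t1/2 = ln 5 / ln 2.

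- With tlast = 44 d, t1/2 = 44 × ln 2 / ln 5 = 18.95 d (18.1 to 19.8 d across the window).
- With t1/2 = 14 d, tlast = 14 × ln 5 / ln 2 = 32.5 d.

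The protocol allows a last sample earlier than 32.5 days. Refusing PK sampling is not a violation (7.3), patients who leave after Day 14 are not replaced (4.3.5), and the final sample then moves to the early termination visit (Appendix 2, footnote c).

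**Step 3: how often, with the Day 45 sample taken.** With σ = √ln(1 + CV²) and z = ln(18.95/14)/σ, the chance per patient is p = 1 − Φ(z). The expected number is 15p, and the chance of at least one is 1 − (1 − p)^15. At CV 30%, σ = 0.294, z = 1.031, p = 0.151, 15p = 2.3 and 1 − 0.849^15 = 0.91.

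| Assumed CV | p per patient | Expected of 15 | At least one |
|---|---|---|---|
| 10% | 0.1% | 0.02 | 2% |
| 15% | 2.1% | 0.3 | 27.5% |
| 20% | 6.3% | 0.9 | 62% |
| 30% | 15.1% | 2.3 | 91% |
| 40% | 21.6% | 3.2 | 97% |

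**Step 4: would the R-squared rule catch these patients anyway?** Not necessarily. A linear-up/log-down calculation at the protocol's sampling times, on noise-free mono-exponential curves, gave R-squared of 1.00 at extrapolated shares from 20% to 67%. If Day 15 is the last sample, at least three points after Cmax can remain, so lambda-z can still be estimated.

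**Step 5: which parameter leans most on the tail.** Vss also uses the first-moment area (AUMC), whose extrapolated share is (1 + kT)·e^(−kT). At a half-life of 19 d and T = 44 d, kT = 44 × ln 2 / 19 = 1.605. Then 20.1% of AUC is extrapolated, but 2.605 × 0.201 = 52% of AUMC.

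**The case against.** The strongest reply is that nothing need happen. At the only half-life in the documents a typical patient passes comfortably, and if nobody exceeds 20% the two sets of patients coincide. The frequencies rest on an assumed CV, and over 10% to 40% they run from about 2% to 97%. This stands: the documents do not show that the mismatch will occur, or that it is likely.

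Several stronger readings are tempting and are not supported.

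- **That CL, Vss and Vz would be summarised for all patients.** They would not. The R-squared rule, the pre-dose rule, the major-deviation rule (SAP 11) and the PK analysis set definition (SAP 5.5) all remove patients or data. The parameters are also computed only where the data permit.
- **That the retained values are shown to be in error.** The check counts how often the rule triggers; it does not measure error in CL, Vss or Vz. In the mono-exponential model the extrapolation is exact. The larger extrapolated share for Vss shows exposure and nothing more.
- **That the mismatch would be hidden.** SAP 19 requires n for each parameter, the shell of Table 14.4.1.2 has an n row, and Listings 16.2.8.7.1 and 16.2.8.7.2 show each patient's values and %AUCex.

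A further objection is that extending the exclusion removes patients selectively, because long half-lives trigger it, and so could shift summarised CL. That is a real cost. The SAP already accepts the same selection for AUC(0-inf), however, so it does not justify summarising CL for patients whose AUC is withheld. Nor does the change equalise every row, because Cmax, AUC(0-last), lambda-z and t1/2 stay in. Those parameters do not use AUC(0-inf), so keeping them is not part of the inconsistency.

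**Conclusion.** The point holds in conditional form. As written, the extrapolation rule withholds AUC(0-inf) and keeps three parameters derived from it, against the SAP's own R-squared rule. If at least one ANB020 patient exceeds 20%, the AUC(0-inf) summary and the CL, Vss and Vz summaries describe different patients, and the latter include values from a withheld AUC.

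A reader might infer that the PK table will certainly be inconsistent, or that the PK objective is compromised. Neither follows. The trigger needs a half-life above about 19 days with the Day 45 sample, or a sample series ending before about 32.5 days at a 14-day half-life. Its probability cannot be fixed from the documents. The named PK endpoints are Cmax and tmax only (Protocol 9.6.1, SAP 17.2.2), and they are unaffected. CL, Vss and Vz are additional descriptive parameters, and no test, dose or efficacy conclusion in the documents depends on them. This is a minor correction.

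**What to change.** In the %AUCex row of SAP 19, name AUC(0-inf), CL, Vss and Vz together as the parameters that "will be listed but not included in summary presentations or analyses", matching the R-squared row. No change to the table shell is needed, and the individual values remain in the listings.

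**Cost.** This is one sentence in the SAP. The n for CL, Vss and Vz may fall by a few patients. Because the patients removed have long half-lives, summarised CL may also shift upward. If all half-life variation comes from CL (an assumption), geometric mean CL rises by a factor exp(σφ(z)/Φ(z)), with σ and z as defined in the working. At CV 30% that is exp(0.294 × 0.2345/0.849) = 1.08. The rise is about 3%, 8% and 15% at assumed CVs of 20%, 30% and 40%. The report should state that the summaries of AUC(0-inf), CL, Vss and Vz are selected in this way.
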